#### 6.4 Missed or Vomited Doses

A missed or vomited dose should not be replaced. The participant will be instructed to take the next scheduled dose at the regularly scheduled time.

#### 6.5 Dose Modifications

When a drug-related toxicity is observed, dose interruptions and/or reductions in miransertib administration are allowed. In general, once the dose of miransertib has been modified for a participant, all subsequent doses should be administered to that participant at the modified dose level. A drug-related toxicity is any toxicity considered related, probably related, or possibly related to miransertib.

Dose reduction should occur according to Table 5. Guidelines for dose interruptions for drug-related toxicities and hyperglycemia are detailed in Table 6 and Table 7, respectively.

Table 5 Miransertib Dose Reduction Schedule

Administered Dose	Dose Reduction
25 mg/m  qd:	15 mg/m² qd
	10 mg/m² qd
	5 mg/m  qd
15 mg/m  qd (during first 3 cycles)	10 mg/m² qd
	5 mg/m  qd

qd=once per day

Dose reduction is allowed and should be performed per Table 5. If the dose reduction is indicated, the participant should be assigned to the lower dose and it should be agreed on by the investigator and the Sponsor. Dose re-escalation will not be permitted.

Treatment will be permanently discontinued in case of Grade 2 drug-related toxicity that does not recover within 21 days after holding miransertib, or Grade 3 drug-related toxicity at the lowest dose (5 mg/m²), or if another discontinuation criterion listed in the protocol is met.

Table 6 Dose Interruptions/Reductions for Drug-Related Toxicity Except Hyperglycemia

Event Grade (CTCAE)	Action
Grade 1	Continue current dose level.
Grade 2	Withhold miransertib until recovery to Grade 1 or baseline. If recovery occurs within 21 days of holding miransertib, restart miransertib at the same dose level, unless further dose reduction is required.
	If a participant experienced a Grade 2 drug-related toxicity that does not recover within 21 days of holding miransertib at a higher dose level (25 mg/m  or 15 mg/m  ), they will be allowed to reduce the dose to the next lower level once the event has recovered to Grade 1 or baseline.
Grade 3-4	Withhold miransertib until recovery to Grade 1 or baseline. If recovery occurs within 21 days of holding miransertib, restart miransertib at the next lower dose level for subsequent doses, unless further dose reduction is required.
	If recovery occurs after more than 21 days on drug hold, permanently discontinue miransertib.

Table 7 Dose Modification for Drug-Related Hyperglycemia and Suggested Clinical Treatment and Management of Hyperglycemia

Event Grade (CTCAE)	Miransertib Dose Modification	Suggested Clinical Treatment and Management of Hyperglycemia
Grade 1		Start once per day home glucose monitoring (alternate between before breakfast and dinner, preferably fasting). No treatment needed.
Grade 2	Grade 1 or baseline.  If recovery occurs within 21 days of holding miransertib, restart miransertib	Start home glucose monitoring twice per day (before breakfast and dinner, preferably fasting).  Treat hyperglycemia per the institutional standard of care.
Grade 3 or 4	Withhold miransertib until recovery to Grade 1 or baseline. If recovery occurs within 21 days of holding miransertib, restart miransertib at the next lower dose level for subsequent doses, unless further dose reduction is required. If recovery does not occur within 21 days of drug hold, permanently discontinue miransertib.	Treat hyperglycemia per the institutional standard of care.

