#### 4.2.1 Discontinuation From Treatment

- Participant experiences, in the opinion of the investigator, an acceleration of the overgrowth disease.
- Miransertib-related clinically significant toxicities that do not recover despite optimal treatment or dose reduction.
- Participant needs to take or elects to take another investigational agent.

• Development of any concurrent medical condition that might preclude or

contraindicate the further administration of miransertib.

- Serious protocol violations such as noncompliance with treatment or required follow-up and evaluation as determined by the investigator.
- Investigator's decision (in agreement with the Sponsor's Medical Monitor or designee).
- Participant, or guardian, refusal of further treatment/withdrawal of consent. Reasons for refusal of further treatment/withdrawal of consent should be noted in that participant's medical record.
- Death.

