4.3.4 Exposure to Study Drug

Exposure to miransertib will be calculated as follows: date of last dosing minus the first day of dosing + 1. The exposure calculation will not take into account breaks in therapy.

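### Protocol Section 6.5 orders a permanent stop for Grade 2 drug-related toxicity not recovered within a 21-day hold, while Table 6 permits the same non-hyperglycemia event at 25 or 15 mg/m² to resume one level lower; the exception is probably intended but is not stated

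*Protocol*

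**What the plan says.** Protocol Section 6.5 gives a stop rule in its text and grade-by-grade actions in two tables.

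- **Text above Table 6:** "Treatment will be permanently discontinued in case of Grade 2 drug-related toxicity that does not recover within 21 days after holding miransertib". The same sentence then adds Grade 3 toxicity at the lowest dose (5 mg/m²) and any other listed discontinuation criterion.
- **Table 6**, titled "Dose Interruptions/Reductions for Drug-Related Toxicity Except Hyperglycemia". Its Grade 2 row takes an event not recovered within 21 days of holding at 25 or 15 mg/m² and says of those participants: "they will be allowed to reduce the dose to the next lower level once the event has recovered to Grade 1 or baseline". Its Grade 3-4 row says: "If recovery occurs after more than 21 days on drug hold, permanently discontinue miransertib".
- **Sponsor involvement:** of an indicated dose reduction, Section 6.5 says "it should be agreed on by the investigator and the Sponsor".
- **Section 4.2.1** lists as a reason to end treatment clinically significant drug-related "toxicities that do not recover despite optimal treatment or dose reduction".

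Section 6.5 introduces Tables 6 and 7 as guidelines for dose interruptions. It does not say whether they qualify the stop sentence.

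**The concern.** One event receives two instructions. A Grade 2 drug-related toxicity other than hyperglycemia, at 25 or 15 mg/m², that recovers after day 21 of the hold leads to a permanent stop under the sentence. Under Table 6 it may lead to a restart one level down. These are the two main planned dose levels in Part B.

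The first stake is participant management. A site that applies the sentence literally ends treatment for someone whom Table 6 would have allowed to continue. If the sponsor in fact means the stricter rule, Table 6 permits re-exposure that should not happen.

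The second stake is the tolerability record, since safety and tolerability are now the only primary objective. The rule that a site follows affects:
- disposition, dose at withdrawal and cycles completed (SAP 4.6);
- whether a restart after day 21 counts as a protocol deviation (SAP 4.7);
- exposure and the count of participants dosed at each level (SAP 4.3.4 and 4.12);
- the discontinuation listing and the treatment-emergent window, which runs to 90 days after the last dose (SAP 4.16).

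**Working it through.** The plan states no figure to reproduce, so the check compares the texts and then works out the smallest effect per participant.

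**Step 1. Same trigger, two actions.**

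| Grade 2, drug-related, not hyperglycemia, recovery after day 21 of hold | Section 6.5 sentence | Table 6 Grade 2 row |
|---|---|---|
| At 25 mg/m² | Permanent stop | May resume at 15 mg/m² |
| At 15 mg/m² | Permanent stop | May resume at 10 mg/m² |
| At 10 or 5 mg/m² | Permanent stop | No allowance, so no conflict |

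The next lower levels come from Table 5. An event that never recovers gets no further drug under either text.

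**Step 2. Could the lowest-dose qualifier govern both limbs of the sentence?** It follows the Grade 3 limb, after a comma and a conjunction. If it also governed the Grade 2 limb, late-recovering Grade 2 toxicity at 10 mg/m² would fall under neither the stop rule nor the Table 6 allowance. At best the wording is ambiguous.

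**Step 3. Is the conflict settled elsewhere?** The synopsis allows delays and reductions in general terms. Protocol 2.2 allows lower doses after toxicity in the first three cycles. Protocol 4.2.1 envisages dose reduction before a stop. The SAP has no dose-modification rule. None of them states the exception.

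**Step 4. Hyperglycemia.** Table 6 excludes it. The Grade 2 dose cell of Table 7 is incomplete in the text available for this check; it breaks off after "If recovery occurs within 21 days of holding miransertib, restart miransertib". No claim is made about hyperglycemia.

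**Step 5. Smallest effect for a participant who resumes.** Let day 0 be the last dose before the hold.
- Held days without recovery: days 1 to 21.
- Earliest recovery and restart: day 22.
- SAP exposure = last dose date − first dose date + 1, and "The exposure calculation will not take into account breaks in therapy".
- Difference in last dose and in exposure: at least 22 − 0 = 22 days, of which 21 are drug-free.
- The treatment-emergent window ends at last dose + 90 days, so its end also moves by at least 22 days.

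This is a floor. It does not depend on when in treatment the hold starts, and any dosing beyond day 22 adds to it.

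**Step 6. Weight of one participant in the Part B cohort columns**, at the planned sizes in SAP 2 and 2.3:
- Cohort 1: 1/20 = 5.0 percentage points
- Cohorts 2 and 4: 1/10 = 10.0
- Cohort 3: 1/25 = 4.0

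These are simply 1/n and would apply to any one-participant change. The actual Safety Population sizes are not in the documents.

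**The case against.** The strongest reply is that the specific text qualifies the general one. The Table 6 paragraph directly follows the sentence and is limited to two dose levels. It would have no function if the sentence overrode it. Read together, the two give a workable scheme: reduce from 25 or 15 mg/m², stop at 10 or 5 mg/m². Section 4.2.1 points the same way. This is probably the intent. It does not remove the problem, because the stop is worded as mandatory and unqualified while the tables are introduced only as guidelines.

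Three further objections stand and limit the point.

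- **Table 6 permits; it does not require.** A reader might infer that a site that stops treatment breaches Table 6, or that Table 6 keeps the participant on drug. The wording is permissive, so stopping is compatible with it, and the error is in the cautious direction.
- **Part A.** A reader might carry the effect over to Part A and the Overall column. No text clearly applies Section 6.5 to Part A. SAP 2 says those participants continue on the schedule they had when Amendment 6 was approved, and those earlier dose-modification rules are not in the documents. No Part A or Overall weight is therefore claimed.
- **Size.** Against a maximum of 48 × 28 = 1,344 days on treatment, the 22-day floor is 22/1,344 = 1.6%. The documents support no larger figure.

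Sponsor agreement on reductions also makes an unnoticed restart unlikely. The sentence attaches no such step to the stop, so a stop based on the sentence alone is the main remaining risk.

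**Conclusion.** The sentence is wrong as written, and the issue is minor and operational. For non-hyperglycemia Grade 2 drug-related toxicity at 25 or 15 mg/m² with recovery after day 21, it mandates a stop where Table 6 permits a lower dose, and the probable exception is unstated. The number of participants affected is unknown and probably small. For each one who resumes, last dose, exposure and window end fall at least 22 days later than under the sentence, and discontinuation and dose-level counts differ. No hypothesis test is involved and no figure in the plan changes.

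The conclusion rests on the literal wording of Section 6.5 and on counting the first missed dose as hold day 1. It does not show that any participant was managed wrongly.

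**What to change.** In the Section 6.5 sentence, directly after the Grade 2 limb, insert: (except where Table 6 or Table 7 allows dose reduction after later recovery). Leave the Grade 3 limb and the rest of the sentence unchanged. Naming both tables is safer than limiting the exception to non-hyperglycemia toxicity, which could contradict the Table 7 Grade 2 cell that could not be read in full here.

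If the sponsor intends the stricter rule, delete the second paragraph of the Table 6 Grade 2 row instead.

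For participants already treated, use the collected dosing and adverse event data to find Grade 2 holds longer than 21 days at 25 or 15 mg/m², and record the action taken. SAP 4.16 plans listings for interruption and discontinuation but none for dose reduction, and it does not specify what the listings contain, so they may not be enough alone.

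The cost is one parenthesis or one deleted paragraph, plus a manual review. No new data collection is needed.

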ARQ 092 in Children and Adults with Proteus Syndrome"; NCT02594215). The primary endpoint of the study was to determine the biological effect of miransertib measured by changes of phosphorylated AKT (pAKT) levels in the affected tissue. Secondary endpoints included safety, tolerability, and disease specific evaluations (volumetric magnetic resonance imaging [MRI], photography of the cerebriform connective tissue nevus [CCTN], quality of life [QoL], and functional assessments). The study initially enrolled 3 adult patients. Once miransertib was shown to be well tolerated, additional 3 younger patients (<18 years of age) were enrolled. All participants were treated at a daily dose of 5 mg/m^2 and were expected to complete 12 cycles of treatment, with a cycle being defined as a 28-day period. Of the 6 enrolled participants, 2 discontinued treatment after 8 cycles (due to withdrawal of consent and an adverse event of transaminase increase), 3 participants completed 12 cycles, and 1 participant continues treatment after completion of 12 cycles. In 5 participants, a reduction of 50% or greater of tissue pAKT levels was reported, and the primary endpoint of the study was met. The clinical efficacy measurements showed reduction in size of the CCTN at Cycle 12 by quantitative standardized photography. The 3 younger participants reported an improvement in pain as assessed by a standardized pain scale. The drug was well tolerated with most adverse events (AEs) being mild to moderate in severity.

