	Participants in Cohort 4 will receive miransertib at the same dose they were on at the time of enrollment, the dose should not exceed 25 mg/m². For participants who previously received miransertib but at the time of the enrollment were not receiving the drug, miransertib administration will follow Part B miransertib administration schedule. Independent from the dose the participant is on, the actual dose should be evaluated at each study visit and adjusted when necessary based on BSA, since it is expected to change over the course of treatment due to the normal growth of the participant.
Criteria for Dose Escalation/ Reduction:	For participants enrolled in Part B Cohorts 1, 2, and 3 dose escalation to 25 mg/m  qd will be performed after 3 cycles of treatment at the initial dose of 15 mg/m  qd provided no clinically significant drug-related toxicity was observed (as assessed by the investigator and agreed on by the investigator and the Sponsor). When a miransertib-related toxicity is observed, dose delays and/or reductions are allowed. Dose re-escalation will not be permitted.
Duration of Treatment:	For an individual participant, treatment will continue for up to 48 cycles or until disease progression, unacceptable toxicity, or another discontinuation criterion is met.  It is expected that most participants will receive between 3 and 48 cycles of treatment.
Data Monitoring Committee:	The DMC will monitor participants' safety by reviewing and evaluating study data, reviewing study conduct and progress, and making recommendations concerning the continuation, modification, or termination of the study. Data Monitoring Committee (DMC) meetings will take place at least 2 times per year.

Statistical Analysis:	All participants who receive at least 1 dose of miransertib will be included in the analysis of safety.
	For Part A and Part B: The safety and tolerability of miransertib for all participants enrolled in Part A and Part B will be determined and summarized as a clinical narrative.
	Further details including data handling rules will be provided in the Statistical Analysis Plan (SAP).

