#### PROTOCOL/AMENDMENT NO.: 002-07

- 4. Grade 2 (per current version of NCI CTCAE) or worse conduction defect (eg, right or left bundle branch block)
- 5. Major surgical procedures or locoregional therapy within 4 weeks of the first dose of miransertib
- 6. Any experimental systemic therapy for the purposes of treating PROS or PS (eg, sirolimus, everolimus, high dose steroids) within 2 weeks of the first dose of miransertib
- 7. Intolerance of or severe toxicity attributed to AKT inhibitors (eg, miransertib, uprosertib, afuresertib, ipatasertib)
- 8. Concurrent severe uncontrolled illness not related to PROS or PS, including:
  - Ongoing or active infection
  - Known HIV infection
  - Malabsorption syndrome
  - Psychiatric illness/substance abuse/social situation that would limit compliance with study requirements
- 9. Pregnant or breastfeeding
- 10. Inability to comply with study evaluations or to follow drug administration guidelines

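### Section 6.5 requires a stop for Grade 3 but not Grade 4 drug-related toxicity at 5 mg/m², so a Grade 4 event there that recovers within 21 days has neither a mandatory stop nor a restart dose

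*Protocol*

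**What the plan says.** The running text of Protocol Section 6.5 gives three grounds for permanent discontinuation: Grade 2 drug-related toxicity that has not recovered after 21 days off drug; "or Grade 3 drug-related toxicity at the lowest dose (5 mg/m²"); and a general clause, "or if another discontinuation criterion listed in the protocol is met".

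Table 6 (toxicities other than hyperglycemia) and Table 7 (hyperglycemia) each handle Grades 3 and 4 in one row. Drug is held until Grade 1 or baseline. If that takes no more than 21 days, the site is to "restart miransertib at the next lower dose level for subsequent doses, unless further dose reduction is required". If it takes longer, drug is stopped for good. Table 5 sets the reduction steps, and 5 mg/m² is the last of them.

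Two other places bear on stopping. Section 4.2.1 lists clinically significant related toxicities that do not recover, and also "Investigator's decision (in agreement with the Sponsor's Medical Monitor or designee"). The synopsis, under duration of treatment, says dosing goes on "until disease progression, unacceptable toxicity, or another discontinuation criterion is met".

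**The concern.** Read as written, the lowest-dose rule is stricter for the less severe event. A participant with a Grade 3 event at 5 mg/m² must come off drug. A participant with a Grade 4 event at the same dose, recovered within 21 days, falls to a table row that points to a dose level that does not exist.

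The literal reading is a fair one because the protocol writes grade ranges elsewhere when it means them. The rows of Tables 6 and 7 name both Grades 3 and 4, and exclusion criterion 4 in Section 3.2 reads "Grade 2 (per current version of NCI CTCAE) or worse conduction defect".

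What is at stake is consistent handling of a severe event. The fallback scale in Section 7.6 describes Grade 4 as life-threatening or disabling. Participants may be as young as 2 years and may be treated for up to 48 cycles. Safety and tolerability is now the primary objective. A site that resumed dosing at 5 mg/m² would have no text permitting it, but would have broken no explicit stopping rule.

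**Working it through.** No formula applies, so the check is to list every Grade 3 or 4 branch and see which have a stated action.

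**Inputs**
- Dose levels, Table 5: 25, 15, 10 and 5 mg/m².
- Grades: 3 and 4.
- Recovery: within 21 days, or later than that.
- Actions: Section 6.5 text, and the Grade 3 and 4 rows of Tables 6 and 7.

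Branches: 4 levels × 2 grades × 2 recovery outcomes = 16.

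| Dose level (mg/m²) | Grade | Recovery within 21 days | Recovery after 21 days |
|---|---|---|---|
| 25 | 3 or 4 | restart at 15 | stop |
| 15 | 3 or 4 | restart at 10 | stop |
| 10 | 3 or 4 | restart at 5 | stop |
| 5 | 3 | stop (Section 6.5 text) | stop |
| 5 | 4 | **nothing stated** | stop |

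Defined at 25, 15 and 10: 3 × 2 × 2 = 12. Defined at 5: Grade 3, 2 branches; Grade 4 with late recovery, 1 branch. Total defined: 12 + 2 + 1 = 15. Open: 16 − 15 = 1. The same branch is open in Table 6 and in Table 7.

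**The open branch against each possible stop**
1. The lowest-dose clause in Section 6.5 names Grade 3 only, so it is not triggered on its wording.
2. The late-recovery stop in Tables 6 and 7 is not triggered, because recovery came in time.
3. The toxicity criterion in Section 4.2.1 concerns toxicities that do not recover, so it is not triggered.
4. The general clause in Section 6.5 refers to other listed criteria. Those that remain are the investigator's decision, which is discretionary, and unacceptable toxicity, which is not defined by grade or dose.
5. The table instruction to restart one level down has no level to go to.

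The same trace for Grade 3 ends in a mandatory stop at step 1.

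**How often.** The documents give neither the number of participants expected at 5 mg/m² nor a Grade 4 rate there. The nearest figure is the earlier Proteus study described in the synopsis, in which all 6 participants were treated at 5 mg/m² daily: "2 discontinued treatment after 8 cycles (due to withdrawal of consent and an adverse event of transaminase increase"). Taking the two reasons as one participant each, 1 of 6 stopped for an adverse event, with its grade not stated. Most adverse events in that study were mild to moderate.

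**The case against.** The strongest reply has three parts.

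First, the clause is probably a floor. In the same sentence the 21-day rule names only Grade 2, yet slow recovery from Grade 3 or 4 also means stopping under the tables. A bare grade in that sentence therefore need not exclude worse ones. This stands as evidence of intent, but not as a rule that a site can point to.

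Second, nothing leads back to dosing. Restart at the same level is written for Grade 2 only, and any reduction needs investigator and Sponsor agreement. A site following the text keeps the participant off drug, which is what the fix would require. This largely stands: no drug is the likely default. It does not make the stop mandatory, and it leaves the tables giving an instruction that cannot be followed.

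Third, the count of 15 out of 16 is not a risk. It weights all branches equally and leaves out the 35 mg/m² level that one Part A participant received, which has no row in Table 5. The 1 of 6 comes from a study in which 5 mg/m² was the dose for everyone, not one reached by reduction after toxicity. All of this is fair. The count shows where the gap is, not how often it will be met.

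The omission is best seen as a drafting slip, not a deliberate choice to be more lenient on Grade 4.

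**Conclusion.** The concern holds. One branch of the dose-modification rules, Grade 4 at 5 mg/m² with recovery within 21 days, has no mandatory stop and no restart dose, for hyperglycemia and for other drug-related toxicities alike. The other 15 Grade 3 and 4 branches are defined.

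This rests on reading the Section 6.5 clause literally and on treating the investigator's decision and unacceptable toxicity as judgments, not automatic stops. The branch is expected to be rare and the likely default is safe. No endpoint, sample size or analysis is touched. It should still be corrected, because a stated safety threshold is stricter for the milder grade than for the more severe one.

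**What to change.** In the discontinuation sentence of Section 6.5, change the grade in the lowest-dose clause from 3 to ≥3. In the Grade 3-4 row of Table 6 and the matching row of Table 7, add: *For an event at 5 mg/m², stop miransertib permanently whatever the time to recovery.*

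The text cost is one changed threshold and two added sentences, with no change to data collection or analysis. It is still a protocol change. Section 10.2 requires written ethics committee approval and, where applicable, approval by the competent authorities before implementation, so it is sensibly combined with the next amendment.
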